## 4.0 INCLUSION AND EXCLUSION CRITERIA

### 4.1 Inclusion

- 4.1.1 Adults  $\geq$  18 years of age
- 4.1.2 Previous history of anti-TB chemotherapy
- 4.1.3 HIV status: HIV infected and uninfected patients are allowed in the study:
  - 4.1.3.1 All patients must agree to HIV testing to confirm HIV status.
  - 4.1.3.2 Patients already on ARVs will be allowed in the study provided that the ART regimen is not contraindicated with any of the study agents (see 4.2.1 below).
  - 4.1.3.3 HIV infected patients at any CD4 count irrespective of ART commencement and duration will be included in the study
- 4.1.4 Smear positive
- 4.1.5 Rifampicin susceptible as determined by Gene Xpert at screening. Gene Xpert will be used to determine Rifampicin resistance, hence the study team will be made aware of resistance prior to study enrolment.
- 4.1.6 Karnofsky score  $\geq$  70
- 4.1.7 Female candidates of reproductive potential must agree to use two reliable methods of contraception while on study: a barrier method of contraception (condoms or cervical cap) together with another reliable form of contraceptive (condoms with a spermicidal agent, a diaphragm or cervical cap with spermicide, an Intrauterine Device (IUD), or hormone-based contraceptive)
- 4.1.8 A negative pregnancy test
- 4.1.9 Laboratory parameters done at, or  $\leq$  14 days prior to, screening:
  - Haemoglobin level of at least 7.0 g/dL
  - Serum aspartate transaminase (AST) and alanine transaminase (ALT) activity less than 3 times the upper limit of normal
  - Serum total bilirubin level less than 2.5 times upper limit of normal
  - Creatinine clearance (CrCl) level greater than 60 ml/min
  - Platelet count of at least  $50 \times 10^9$  cells/L
  - Serum potassium greater than 3.0 mmol/L

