## **Withdrawal from the study**

Patients withdrawn from study due to a protocol violation will be included in the safety database of the study. Patients withdrawn from study because their initial TB isolate is found to be MDR –TB will not be followed up further, unless required for patient safety (e.g. an adverse event present, in which case follow-up should occur as clinically indicated). Similarly, patients withdrawn from study because their initial cultures are negative do not need to be followed up further (unless there is an ongoing adverse event). Participation in the study is strictly voluntary. A participant has the right to withdraw from the study at any time for any reason. Patients who withdraw their consent will not have to undergo any follow up procedures.

This study will be reviewed by a Safety Monitoring Committee (SMC) that meets for scheduled reviews of studies every year. A full SMC review will include an efficacy review and a futility review for detecting a survival difference. A full review will be scheduled at least annually after opening to accrual or on a frequency determined by the SMC. For each full review, summaries provided to the SMC will be broken down by treatment arm. Participants' baseline demographic and health characteristics will be summarized. Review of study conduct will address site accrual, premature study discontinuations and their reasons (administrative or loss to follow-up), tracking of potential losses to follow-up, data completeness. The SMC will also review participants' safety data, frequency and causes of death, as well as incidence of TB recurrence.

In addition, quarterly internal reviews of patient charts, SAE reports and regulatory submissions will be conducted.

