## **9.0 STATISTICAL CONSIDERATIONS**

### **9.1 Sample size determination:**

A total of 330 patients will be enrolled. A two group continuity corrected chi square test with a 0.05 two-sided significance level will have 80% power to detect the difference between 75% of patients having culture conversion in the Intervention arm and 60% of patients having culture conversion in the Control arm. A previous unpublished retrospective review at the study site comparing the treatment outcome in retreatment

patients with TB using the standard 4 drug regimen, showed a cure and completion rate of 60.1%. According to WHO surveillance data, the retreatment regimen is successful in about 70% of patients, and other retrospective studies show treatment success rates of 26 – 92%. Thus, 75% is a realistic cure and completion rate to aim for in the Intervention group. A previous unpublished retrospective review at the study site comparing the treatment outcome in retreatment patients with TB using the standard 4 drug regimen, showed a cure and completion rate of 60.1%. According to WHO surveillance data, the retreatment regimen is successful in about 70% of patients, and other retrospective studies show treatment success rates of 26 – 92%. Thus, 75% is a realistic cure and completion rate to aim for in the Intervention group.

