##### Intention-to-treat population

This population consists of all participants enrolled and randomised to the intervention and control arms. Individuals who will be identified as ineligible for enrolment based on criteria pre-randomisation criteria will be excluded. Moreover, individuals with no post-randomisation visit and no data collected will be excluded.

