## 6.3. Primary objective

*To determine if a Moxifloxacin-containing regimen, [Isoniazid (H), Rifampicin (R), Pyrazinamide (Z), Moxifloxacin (M)] of 24 weeks duration is superior to a control regimen [Isoniazid (H), Rifampicin(R), Pyrazinamide (Z), Ethambutol (E)] of 24 weeks duration in improving treatment outcomes in patients with recurrent TB.*

To answer the primary objective of this study the culture conversion rates will be compared between the two treatment arms at the end of the intensive phase and at month 6, where culture conversion is defined as the first of two negative (or no growth) cultures at two different visits without an intervening positive culture. This will be done by calculating the proportion of culture conversions in each of the two arms and at each of the two time points and comparing these using the chi-square test or Fisher's exact test. Log binomial regression

or Poisson regression with robust variance will also be used to improve precision of the treatment effect estimates.

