#### **6.4. Secondary objective 1**

*To determine the time to culture-conversion of the Moxifloxacin regimen and the Ethambutol regimen using data from 2-, 4-, 6-, and 8-week cultures*

Time to culture conversion is defined as the time from treatment initiation to the date of the first of two negative cultures at two different visits without an intervening positive culture. Kaplan–Meier curves and the Gehan-Breslow-Wilcoxon test will be used to compare time to culture conversion across the two arms. Proportional hazards regression will also be used to assess whether time to culture-conversion differs across the two arms.

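### Culture conversion is defined without a positive baseline culture, and the SAP does not say how participants with a negative baseline culture are scored

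*SAP*

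**What the plan says.** **Endpoint.** In SAP 6.3, "culture conversion is defined as the first of two negative (or no growth) cultures at two different visits without an intervening positive culture". SAP 6.4 measures the "time from treatment initiation to the date of the first of two negative cultures at two different visits", again with no intervening positive. Neither section requires a positive culture at the start. SAP 6.6 compares conversion between HIV groups and gives no definition of its own.

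**Entry.** Protocol 4.1 lists "Smear positive" and rifampicin susceptibility on GeneXpert. A positive culture is not listed. The screening section (7.2.1) confirms TB by smear and GeneXpert, and the schedule of events (Table 5) shows the first culture at baseline, the visit at which participants are randomised.

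**Withdrawal.** The protocol foresees enrolees without a positive culture: "patients withdrawn from study because their initial cultures are negative do not need to be followed up further", unless an adverse event is ongoing. It does not make this withdrawal mandatory or give it a time limit.

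**Analysis set.** The SAP's intention-to-treat definition begins: "This population consists of all participants enrolled and randomised to the intervention and control arms". It removes only those ineligible on pre-randomisation criteria and those with no post-randomisation visit and no data. The per-protocol set deals only with treatment interruption. SAP section 5 ignores missing data by default.

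**Contrast.** The protocol's definitions of cure and treatment failure each require a positive baseline smear or culture. The conversion definition has no such condition.

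**The concern.** Conversion should mean a change from positive to negative. As written, the rule can score a participant who never had a positive culture as a converter, and that participant says nothing about whether either regimen clears the organism from sputum. A positive smear at entry does not supply the missing condition for an endpoint based on culture.

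The withdrawal provision adds a second uncertainty. A participant with a negative baseline culture who stays on study, or who gives two negative cultures before withdrawal, meets the definition. One withdrawn sooner may be missing, or may be a non-converter if kept in an all-randomised denominator. This affects the primary endpoint, and in an open-label trial the choice should be fixed in the plan before results by arm are seen.

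**Working it through.** **Inputs.** Protocol 9.1: "75% of patients having culture conversion in the Intervention arm and 60% of patients having culture conversion in the Control arm"; "A two group continuity corrected chi square test with a 0.05 two-sided significance level will have 80% power to detect the difference"; "A total of 330 patients will be enrolled". Allocation is 1:1 (SAP section 2), so 165 per arm. The share b of participants with a negative baseline culture is not in the documents. I assume 5, 10 and 15%, equal in both arms.

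**Step 1: reproduce the plan's figure.** Let d = 0.15 and the mean rate = 0.675.

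Uncorrected m = [1.960·√(2 × 0.675 × 0.325) + 0.842·√(0.75 × 0.25 + 0.60 × 0.40)]² / 0.15² = (1.298 + 0.550)² / 0.0225 ≈ 151.9, or 152 per arm.

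With the continuity correction, n = (m/4)·[1 + √(1 + 4/(m·d))]² ≈ 164.9, or 165 per arm and 330 in total. The stated size reproduces exactly, and corrected power at 165 per arm is 80.0%.

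**Step 2: three ways to score the share b.**

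- Converters: each rate becomes b + (1 − b)p, so the difference is 0.15(1 − b).
- Excluded (analysis restricted to baseline-positive participants): rates stay at 75% and 60%, with 165(1 − b) per arm.
- Non-converters: each rate becomes (1 − b)p, and the difference is again 0.15(1 − b).

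**Step 3: corrected power.** Inverting the correction gives an effective size m = (√n − 1/(d√n))². Power is then Φ{[d√m − 1.960·√(2p̄q̄)] / √(p₁q₁ + p₂q₂)}.

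Worked at b = 10%:

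- Converters: 77.5% v 64.0%, d = 0.135, m = (12.845 − 0.577)² ≈ 150.5. Power = Φ[(1.656 − 1.261)/0.636] = Φ(0.621) = 73.3%.
- Restricted: 148.5 per arm, d = 0.15, m = (12.186 − 0.547)² ≈ 135.5. Power = Φ[(1.746 − 1.298)/0.654] = Φ(0.685) = 75.3%.
- Non-converters: 67.5% v 54.0%, d = 0.135. Power = Φ[(1.656 − 1.353)/0.684] = Φ(0.443) = 67.1%.

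| Assumed b | Rates if converters | Difference (points) | Power, converters | Power, restricted | Power, non-converters |
|---|---|---|---|---|---|
| 0% | 75.0 v 60.0 | 15.0 | 80.0% | 80.0% | 80.0% |
| 5% | 76.3 v 62.0 | 14.3 | 76.8% | 77.8% | 73.6% |
| 10% | 77.5 v 64.0 | 13.5 | 73.3% | 75.3% | 67.1% |
| 15% | 78.8 v 66.0 | 12.8 | 69.6% | 72.6% | 60.7% |

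At b = 10% the risk ratio is 0.775/0.640 = 1.21 if they count as converters, against 0.75/0.60 = 1.25 among baseline-positive participants.

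**The case against.** The strongest reply is that the gap may be small. These participants are smear-positive and GeneXpert-tested, and Protocol 4.2.3 excludes anyone who received an antibiotic active against the organism in the last 14 days, which limits culture negativity due to earlier treatment. At b = 3% the difference is still 14.6 points, and restriction gains under one point of power (78.1% v 78.7%). The dilution runs toward no difference, so it does not favour a superiority claim. Restriction also leaves power below the stated 80%. All of this stands. It limits the size of the problem but does not say how these participants are scored.

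Three stronger readings are tempting, and the documents do not support them.

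- **A reader might infer that every such participant counts as a converter from the start.** The withdrawal provision means that some may never supply two negatives, so they can count as converters but need not.
- **A reader might infer events at day 0 in the time-to-conversion analysis.** The objective stated in SAP 6.4 uses the 2-, 4-, 6- and 8-week cultures, and baseline is not among them.
- **A reader might infer that chance imbalance creates a spurious treatment difference.** At b = 10% the SD of the imbalance in patient share is √(2 × 0.1 × 0.9/165) = 3.3 points, but each such participant moves the rate only by (1 − p). The SD on the rate difference is √[(0.1 × 0.9/165)(0.40² + 0.25²)] = 1.1 points. This is ordinary sampling error within a standard error of √(0.404775/165) = 5.0 points, and the two-sided 5% test already allows for it.

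Nor does any passage suggest that withdrawal would differ by arm.

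**Conclusion.** The point holds as a gap in the primary endpoint definition. SAP 6.3 and 6.4 allow a participant who was never culture-positive to be a converter, and nothing in the SAP reconciles that with the protocol's withdrawal provision or with the intention-to-treat set. The direction of the effect on the reported conversion rates is therefore not fixed by the documents.

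The size is modest and depends on b, which is assumed. At b = 10%, the choice of handling alone moves corrected power between 67.1% and 75.3%. Restriction recovers about 1 to 3 points over counting them as converters for b of 5 to 15%, so the main case for it is an endpoint that means what its name says. These figures assume that b is equal in both arms and that the planned 75% and 60% apply to baseline-positive participants. Restriction preserves the randomised comparison provided that the baseline culture comes from sputum taken before treatment.

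**What to change.** In SAP 6.3, 6.4 and 6.6:

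- Make the primary conversion analysis all randomised participants whose baseline culture grew *M. tuberculosis*, applied identically in both arms.
- Count only post-baseline cultures toward the two negatives. Section 6.4 already points this way; 6.3 does not.
- Report the number with a negative baseline culture by arm, including how many were withdrawn for that reason, and keep them in the safety analyses.
- Give the all-randomised conversion analysis as a sensitivity analysis, stating how participants withdrawn for negative initial cultures are scored in it.

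The protocol's withdrawal provision and the SAP's analysis sets should be cross-referenced so that they agree.

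The cost is SAP wording, since the baseline culture is already scheduled in both arms. The downside is a smaller primary denominator, lower reported conversion rates, and power slightly below the stated 80% at 330. Holding 80% under restriction would need 348, 367 or 389 enrolled at b = 5, 10 or 15% (330/(1 − b), rounded up). If these participants were counted as converters, the figures would be 356, 384 and 416.

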## 5.0 RANDOMIZATION PROCEDURES

Patients will be randomized to the two arms using permuted block randomization (e.g. blocks of variable sizes 4 or 6) stratified by HIV status. The randomization will be done by a statistician and the randomization codes will not be available to study staff until the participant is randomized. This will be done by providing sealed opaque randomization envelopes to the research staff at the CAPRISA – eThekweni CRS. The envelopes will be stored in a locked cupboard and opened in sequential order by study team members authorized to perform randomization procedures by the Principal Investigator. After opening the envelopes, staff will record the date and time of opening the envelope and their staff details. The patient’s allocated arm will then be recorded on a randomization log.

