## 5. GENERAL STATISTICAL ISSUES

All tests will be two-sided, and the significance level will be 0.05.

Outliers will be identified by looking at summary statistics and scatter plots. All outliers detected will be verified from the source documentation. Outliers that have biologically impossible values will be excluded from all data summaries and analyses. If one (or several) outlier(s) change(s) the interpretation of the data substantially, two summaries and analyses will be done, one with and one without the outlier(s).

If a participant has missing data at a specific time point, data at all non-missing time points for the participant will be used and included in the summaries. Missing data will be ignored (i.e. treated as missing at random) unless patterns are identified which would potentially bias analysis results.

Where applicable, analyses will be stratified by HIV status.

All statistical analyses will be done using SAS (SAS Institute Inc., Cary) version 9.4 or higher.

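### The HIV randomisation stratum is not carried into the primary test in SAP 6.3, and the regression meant to improve precision names no covariates

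*SAP*

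**What the plan says.** - **Randomisation.** Protocol 5.0 uses permuted blocks "stratified by HIV status".
- **Primary test.** SAP 6.3 calculates the proportion converting in each arm at each of two time points, "comparing these using the chi-square test" or Fisher's exact test. Protocol 9.2 names the chi-square test alone. Neither section mentions the stratum.
- **Supporting model.** SAP 6.3 says that log-binomial regression, or Poisson regression with robust variance, "will also be used to improve precision of the treatment effect estimates". It lists no covariate.
- **General clause.** SAP 5 states: "Where applicable, analyses will be stratified by HIV status". It does not say which analyses are meant, or by what method.
- **Covariates elsewhere.** SAP 6.2 asks for a rationale for cut points if categorised continuous variables enter a model, so adjusted models are foreseen. It lists baseline measures (among them BMI, HIV status and number of previous TB episodes) but assigns none to the primary model.
- **A stratified test where one is intended.** SAP 6.6 names the CMH test, stratified by study arm, for the comparison of HIV-positive with HIV-negative patients.
- **Design.** Protocol 9.1 sets the size at 330 and gives the test behind that number: "A two group continuity corrected chi square test with a 0.05 two-sided significance level will have 80% power". On the error rate, SAP 5 agrees: "All tests will be two-sided, and the significance level will be 0.05".

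**The concern.** Stratified randomisation balances HIV status between arms, so the difference in conversion proportions varies less than a simple two-sample formula assumes. A pooled chi-square does not use that balance, and its standard error is somewhat too large if HIV status affects conversion. An analysis that follows the randomisation recovers the loss.

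The second issue is internal. The regression is given one purpose, better precision, and only baseline covariates could deliver it. With none named, either the purpose cannot be met or the covariates will be chosen later. The trial is open label, and SAP 6.3 also leaves open chi-square or Fisher's exact, and log-binomial or Poisson. Two statisticians following this text could report different primary p-values and risk ratios.

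**Working it through.** **1. The plan's own figure.** Inputs from Protocol 9.1: 75% v 60%, two-sided 0.05, 80% power, continuity-corrected chi-square.

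Uncorrected n per arm = [1.96·√(2·0.675·0.325) + 0.8416·√(0.60·0.40 + 0.75·0.25)]² / 0.15² = (1.2983 + 0.5503)² / 0.0225 = 151.9, so 152.

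Corrected n = (151.9/4)·[1 + √(1 + 4/(151.9·0.15))]² = 164.9, so 165 per arm, 330 in total. The stated figure reproduces. Power at 165 per arm is 80.0% with the continuity correction and 83.2% without. The calculation takes no account of a stratum, and stratifying the test does not change it.

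**2. A regression on arm alone.** Take illustrative counts at the design rates: 124/165 v 99/165.

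- log RR = ln(124/99) = 0.2252
- SE from the 2×2 table = √(1/124 − 1/165 + 1/99 − 1/165) = √0.006044 = 0.0777
- log-binomial fit, arm only: 0.2252, SE 0.0777
- robust Poisson fit, arm only: 0.2252, SE 0.0777

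No precision is gained unless covariates enter.

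**3. The cost of leaving HIV out of the test.** The effect of HIV on culture conversion is not in the documents, so it is assumed over a range. The share HIV-infected is 69% (Protocol 3.1, all TB patients at the site). Simulation used 200,000 trials per scenario with 165 per arm and HIV strata balanced between arms. Overall conversion was 60% v 60% (null) or 60% v 75%. Neither test carried a continuity correction.

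| Assumed odds ratio, HIV-infected v uninfected | Type I, chi-square | Type I, CMH | Power, chi-square | Power, CMH | SE of log RR, HIV-adjusted ÷ unadjusted (60% v 75%) |
|---|---|---|---|---|---|
| 1.0 | 0.0503 | 0.0502 | 0.8355 | 0.8343 | 1.000 |
| 0.7 | 0.0485 | 0.0487 | 0.8348 | 0.8352 | 0.997 |
| 0.5 | 0.0471 | 0.0489 | 0.8363 | 0.8394 | 0.991 |
| 0.33 | 0.0435 | 0.0497 | 0.8387 | 0.8469 | 0.979 |
| 0.2 | 0.0377 | 0.0495 | 0.8455 | 0.8626 | 0.962 |

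The largest power difference is 86.26 − 84.55 = 1.7 points.

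**4. Hand check of the last row.** At odds ratio 0.2 and 60% overall, conversion is 0.831 in uninfected and 0.496 in infected patients. The mean within-stratum variance is 0.31·0.831·0.169 + 0.69·0.496·0.504 = 0.216, against a pooled variance of 0.60·0.40 = 0.240. The true SE is √(0.216/0.240) = 0.949 of the one that the pooled test uses. Its real type I error is therefore about 2·[1 − Φ(1.96/0.949)] = 0.039, in line with the simulated 0.038.

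**5. Where in the range the trial may lie.** The only pointer is a proxy. Protocol 1.1 cites a Ugandan cohort on the streptomycin-containing retreatment regimen, with unsuccessful outcome in 20% of HIV-uninfected and 26% of HIV-infected patients. As odds of success this is (0.74/0.26)/(0.80/0.20) = 0.71, close to the 0.7 row, where the two tests have the same power to within 0.1 point. The endpoint and regimen differ from this trial's.

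**6. A different share of HIV.** Protocol 1.1 also quotes 53% HIV co-infection among retreatment cases. At 53% and odds ratio 0.2, type I error is 0.036 for the chi-square, and power is 84.97% v 87.53%, a loss of about 2.6 points.

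**The case against.** **The SAP does not disregard HIV.** A reader might infer that it does. The SAP 5 clause can fairly be read as covering the primary analysis, so that inference goes too far. What stands is that the clause names no analysis and no method, could equally mean separate tables by HIV status, and is not taken up in SAP 6.3, although SAP 6.6 spells out a stratified test where one is wanted.

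**The regression may well be meant to be adjusted.** Its stated purpose and the covariate rule in SAP 6.2 point that way. To say that it cannot improve precision is therefore too strong; that is true only of an arm-only fit. The supportable statement is that no covariates are named.

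**The pooled chi-square is coherent with the design.** It matches Protocol 9.2 and the test family used for sample size. This is correct, and the test is valid: type I error is not inflated at any point of the assumed range.

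**The gain is slight.** This is also correct. At odds ratio 1.0 the stratified test gains nothing, and at 0.5 it gains 0.3 points. A reader might expect more from adding other prognostic factors, but the documents give neither the prevalence nor the effect of any such factor on conversion, so no figure can be claimed.

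**Conclusion.** The point holds as a low-cost improvement to the primary analysis, not as an error that threatens the result. The test named in SAP 6.3 does not follow the stratified randomisation, and the regression as written does not say how it would achieve its purpose.

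With 69% HIV-infected and an assumed HIV odds ratio between 1.0 and 0.2, the pooled test is slightly conservative (type I error 0.050 to 0.038) and gives up from nil to about 1.7 points of power. The 330 patients remain right. These sizes rest on the assumed odds ratio, on a site-wide HIV share applied to retreatment patients, and on the uncorrected chi-square. The main reasons to act are agreement with the randomisation and a primary analysis fixed in advance; recovered power is secondary.

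**What to change.** In SAP 6.3:

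1. Make the primary test the CMH test stratified by HIV status, and report an HIV-stratified risk difference with 95% CI.
2. State that the regression includes arm and HIV status, plus named baseline measures from SAP 6.2, for example BMI and number of previous TB episodes. Make robust Poisson the fallback if the log-binomial model does not converge.
3. Keep the crude chi-square as a sensitivity analysis.

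In SAP 5, list the analyses that the HIV clause covers.

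Smear result should not be listed as a covariate: Protocol 4.1.4 requires every participant to be smear positive, so it could help only if smear grade is recorded.

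The cost is mostly wording. Because Protocol 9.2 names the chi-square, the change must be documented as a departure from it. A rule is also needed for missing covariate values. No further patients, visits or data are required.
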